3.5.1 Additional Discontinuation Criteria - Nivolumab/Daratumumab Cohorts

In addition to the criteria defined above, subjects in the nivolumab/daratumumab cohorts (Cohort A and B) must discontinue study treatments for any of the following reasons:

- Confirmed progressive disease according to IMWG criteria ([Appendix 3](#)).
- Subjects who receive any non-protocol specified systemic anti-myeloma therapy before documented progression will be discontinued from all study treatment; however, tumor assessments will continue at 4-week intervals until documented progression.

- Subjects experiencing a Grade 4 infusion reaction related to daratumumab must discontinue daratumumab. Subjects may continue nivolumab with or without pomalidomide and dexamethasone treatment. Refer to [Section 4.1.5.2](#) for additional reasons to discontinue daratumumab dosing permanently.
- Subjects experiencing treatment related angioedema, Grade 4 rash, exfoliative or bullous rash, Stevens Johnson syndrome, or toxic epidermal necrolysis must discontinue pomalidomide and nivolumab. Subjects may continue on daratumumab and dexamethasone.
- Subjects experiencing \geq 8-week delay in all study drugs (nivolumab, daratumumab, pomalidomide, and dexamethasone) due to an AE(s) related to study treatment must be discontinued from all study treatment. Subjects experiencing delays unrelated to study therapy, for example due to radiation therapy, may delay study treatment up to 84 days. Further delays may be allowed after discussion with the BMS Medical Monitor.
- Subjects experiencing a Grade 4 or the third occurrence of a Grade 3 daratumumab infusion reaction must permanently discontinue daratumumab
- Subjects experiencing a Grade 3 or 4 infusion reaction related to nivolumab must discontinue nivolumab. Subjects may continue daratumumab with or without pomalidomide and dexamethasone treatment. Refer to [Section 4.1.5.1](#) for additional reasons to discontinue nivolumab dosing permanently.

Continuation of study treatments in the circumstance of one or more study treatments being discontinued or delayed should follow these criteria:

- Subjects who experience AEs that require discontinuation of daratumumab may be allowed to continue therapy with nivolumab, with or without pomalidomide and dexamethasone, if deemed in their best interest by both the PI and the BMS medical monitor. Subjects must be deriving clinical benefit.
- Subjects who experience AEs that require discontinuation of nivolumab may be allowed to continue therapy with daratumumab, with or without pomalidomide and dexamethasone, if deemed in their best interest by both the PI and the BMS medical monitor. Subjects must be deriving clinical benefit.
- Subjects who experience AEs that require discontinuation of nivolumab and daratumumab in the ND-Pd arm may be allowed to continue therapy with pomalidomide and dexamethasone, if deemed in their best interest by both the PI and the BMS medical monitor. Subjects must be deriving clinical benefit.
- Subjects who experience AEs that require discontinuation or delay of pomalidomide in the ND-Pd arm may be allowed to continue therapy with nivolumab, daratumumab, and dexamethasone, if deemed in their best interest by both the PI and the BMS medical monitor. Subjects must be deriving clinical benefit.
- Subjects who experience AEs that require discontinuation or delay of dexamethasone in the ND-Pd arm may be allowed to continue therapy with nivolumab, daratumumab, and pomalidomide, if deemed in their best interest by both the PI and the BMS medical monitor. Subjects must be deriving clinical benefit.

All subjects who discontinue should comply with protocol specified follow-up procedures as outlined in [Section 5](#). The only exception to this requirement is when a subject withdraws consent for all study procedures or loses the ability to consent freely (ie, is imprisoned or involuntarily incarcerated for the treatment of either a psychiatric or physical illness).

If a subject was withdrawn before completing the study, the reason for withdrawal must be entered on the appropriate case report form (CRF) page.

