In addition to administering a full dose of 16 mg/kg on Cycle 1 Day 1, “split-dosing” of daratumumab (ie, 8 mg/kg on Cycle 1 Day 1 and 8 mg/kg on Cycle 1 Day 2) can be utilized for Cohort B at the investigator’s discretion. The first split-dose infusion will be prepared as a 500-mL dilution of 8 mg/kg of daratumumab given on Days 1 and 2 of Cycle 1. If these 2 infusions are well-tolerated (absence of > Grade 1 IRR), the second week of daratumumab will be given as a 16 mg/kg dose diluted in 500 cc of normal saline. If the first 2 doses of daratumumab are not well-tolerated (defined as > Grade 1 IRR), then the second week of daratumumab will be given as 16 mg/kg in 1000 mL on Cycle 1 Day 8. From Cycle 1 Day 15 and beyond, the dose of daratumumab will not be split and will be the standard 16-mg/kg dose. The dilution will be in 1000 cc of normal saline until the subject completes an infusion without > Grade 1 IRR. For all infusions, daratumumab will be prepared in sterile, pyrogen free 0.9% NaCl. Preparation of the infusion bags should be done on the day of the planned infusion. Daratumumab must be administered as an IV infusion given through a well-functioning IV catheter by using an infusion pump. The study drug must be filtered by using an inline filter (0.2 µM) during the infusion. Manuals with detailed descriptions for preparation and administration of daratumumab will be supplied to each pharmacy and site.

Infusion-related supplies (eg, IV bags, in-line filters, 0.9% NaCl solution, pump) will not be supplied by the sponsor and should be purchased locally if permitted by local regulations.

When more than one study drugs are to be administered as IV infusion on the same day, separate infusion bags and filters must be used for each infusion. Nivolumab is to be administered first. The nivolumab infusion must be promptly followed by a saline flush to clear the line of nivolumab before starting the daratumumab infusion. The second infusion will always be daratumumab and will start no sooner than 30 minutes after completion of the nivolumab infusion.

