4.1.4 Selection and Timing of Dose for Each Subject

4.1.4.1 Nivolumab

Cohort A

- Nivolumab will be administered at a dose of 240 mg as an intravenous infusion over 30 minutes on Day 15 during Cycle 1, and on Days 1 and 15 during Cycles 2 through 6 (ie, every 2 weeks of each 28-day cycle). Starting Cycle 7 and beyond, nivolumab will be administered at a dose of 480 mg as an IV infusion over 30 minutes every 4 weeks (Day 1 of each 28-day cycle).
- Nivolumab can be delayed within a 3-day window of Day 1 and Day 15, during Cycles 1 through 6, as long as the 12-day interval between 2 nivolumab doses is respected. During Cycles 7 and beyond, nivolumab can be delayed within a week, as long as the 21-day interval between 2 nivolumab doses is respected. Doses that fall outside the allowed window should be skipped.

Cohort B

- Patients randomized to ND treatment (only): nivolumab will be administered at a dose of 240 mg as an intravenous infusion over 30 minutes on Day 15 of Cycle 1. Starting Cycle 2 and beyond, nivolumab will be administered at a dose of 480 mg as an intravenous infusion over 30 minutes every 4 weeks (Day 1 of each 28 day cycle).
- Cycle 1 dose (C1D15) can be delayed within a 3 day window from Day 15. Doses that fall outside the allowed window should be skipped.
- From Cycle 2 (C2D1) and beyond, nivolumab can be delayed within in a 7 day window of Day 1, as long as the 21-day interval between two 480 mg nivolumab doses is respected, and a 12-day interval between C1D15 and C2D1 is respected. Doses that fall outside the allowed window should be skipped.

Nivolumab should be administered before daratumumab. There are no pre-medications recommended for nivolumab.

Subjects should be carefully monitored for infusion reactions during nivolumab administration. If an acute infusion reaction is noted, subjects should be managed according to [Section 3.4.2.1](#).

There will be no dose escalations or reductions of nivolumab allowed. Doses of nivolumab may be interrupted, delayed, or discontinued depending on how well the subject tolerates the treatment.

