4.1.4.2 Daratumumab

Daratumumab will be administered at a dose of 16 mg/kg as an IV infusion every week (Days 1, 8, 15, and 22 of each 28-day cycle) during Cycles 1 and 2. As an option, in Cycle 1, the first full dose of daratumumab at 16 mg/kg may be split into 2 doses at 8 mg/kg and administered via IV on Cycle 1 Days 1 and 2. From Cycles 3 through 6, daratumumab will be administered every 2 weeks (Days 1 and 15 of each 28-day cycle), then starting Cycle 7 and beyond, daratumumab will be administered every 4 weeks (Day 1 of each 28-day cycle). The infusion rates should closely follow the specifications of the currently approved (USPI)/pharmacy reference manual.⁹⁸

All infusions will be planned as outpatient visits. Subjects will receive preinfusion medications and postinfusion medications as detailed in the protocol.

Daratumumab should be administered after nivolumab.

MM subjects randomized to the ND or D regimens will receive pre- and post-infusion medication for daratumumab infusion per the daratumumab label, as described (in [Section 3.4.1.4](#)).

MM subjects randomized to ND-Pd regimen will receive the treatment regimen dexamethasone dose split as IV pre-infusion and oral post-infusion on weeks with daratumumab infusions, and only oral in the weeks without daratumumab infusion (see [Section 4.1.4.4](#)). No additional corticosteroids besides the dexamethasone dose included in the treatment regimen will be administered to the ND-Pd subjects.

The dilution volumes and infusion rates for C1D1 (16 mg/kg), and optional split-dosing of C1D1 (8 mg/kg) and C1D2 (8 mg/kg), C1D8 (16 mg/kg), and subsequent infusions are provided in [Table 4.1.4.2-1](#). The sponsor may modify the infusion rates or the preinfusion medications prospectively based upon the information collected to date from this and other studies. Additional details for administration times and rates, as well as preinfusion medications, will be provided in the administration guidelines (study site investigational product and procedures manual/package insert).

Table 4.1.4.2-1: Daratumumab Infusion Rates

	Dilution Volume	Initial Infusion Rate (first hour)	Increments of Infusion Rate	Maximum Infusion Rate
C1D1 (16 mg/kg single dose)	1000 mL	50 mL/hour	50 mL/hour every hour	200 mL/hour
Optional split-dosing: C1D1 and C1D2 (8 mg/kg split dose)	500 mL	50 mL/hour	50 mL/hour every hour	200 mL/hour

Table 4.1.4.2-1: Daratumumab Infusion Rates

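### The severe skin and angioedema rule in Protocol 3.5.1 was not adapted to Cohort B: it allows daratumumab to continue even when daratumumab is the suspected cause

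*Protocol*

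**What the plan says.** The lead-in to Protocol 3.5.1 makes its list binding on Cohorts A and B. One item reads "Subjects experiencing treatment related angioedema, Grade 4 rash, exfoliative or bullous rash, Stevens Johnson syndrome, or toxic epidermal necrolysis must discontinue pomalidomide and nivolumab", followed by "Subjects may continue on daratumumab and dexamethasone". The trigger is relatedness to treatment in general; no drug is named.

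The infusion-reaction items in the same list are drafted differently. Each names the drug and stops that drug: "Subjects experiencing a Grade 4 infusion reaction related to daratumumab must discontinue daratumumab" and "Subjects experiencing a Grade 3 or 4 infusion reaction related to nivolumab must discontinue nivolumab".

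Cohort B randomizes about 60 subjects 2:1 to nivolumab plus daratumumab (ND) or daratumumab alone (D) (Synopsis; 3.1). Neither arm contains pomalidomide, and the D arm has no nivolumab.

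**The concern.** The item suits the ND-Pd regimen of Cohort A, where pomalidomide and nivolumab are both present. Carried over to Cohort B unchanged, it controls the two drugs it was written for and gives permission for the third, whatever the suspected cause.

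The consequence is a safety rule that does not require the suspected drug to be stopped, in a cohort whose primary objective is tolerability. Sites could handle the same event differently, some following the permission and others overriding it on judgement. No efficacy estimate, sample size or error rate is affected.

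**Working it through.** There is no planned figure to reproduce. The check sets the rules side by side and asks what each requires when daratumumab is the suspected cause.

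**Arm sizes.** With about 60 subjects at 2:1, ND is 60 × 2/3 = 40 and D is 60 × 1/3 = 20. The D share is 20/60 = 33%. This is the share of subjects for whom the mandatory half is empty, not a risk of an event.

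**What the 3.5.1 item does.**

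| Arm | Drugs it stops that the subject receives | Position of daratumumab |
|---|---|---|
| ND (about 40) | Nivolumab | May continue |
| D (about 20) | None | May continue |

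**Does another section narrow the trigger?** Section 6 defines causality only against study drug, without attribution to a single agent. It does not limit the item to events caused by nivolumab or pomalidomide.

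**Can daratumumab be the suspect when nivolumab is not?** In the D arm this is always so. In the ND arm it is so at the start. Section 4.1.4.2 schedules daratumumab at "16 mg/kg as an IV infusion every week (Days 1, 8, 15, and 22 of each 28-day cycle) during Cycles 1 and 2", while 4.1.4.1 states that "nivolumab will be administered at a dose of 240 mg as an intravenous infusion over 30 minutes on Day 15 of Cycle 1". On a shared day, 4.1.3 says "Nivolumab is to be administered first". The doses on Days 1 and 8 therefore come before any nivolumab: 2 doses, or 3 infusions if the first is split. If the Day 15 nivolumab dose is skipped, daratumumab on Days 1, 8, 15 and 22 makes 4 doses before Cycle 2 Day 1.

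**What 4.1.5.2 requires of daratumumab.**
- Delay for non-hematologic toxicity from Grade 3 upward. The exceptions are gastrointestinal events and fatigue or asthenia, so severe skin events are covered by the delay.
- Restart once the event is back to Grade 2 or baseline. Laryngeal edema and bronchospasm must recover fully.
- Permanent stop if a related hold exceeds 4 × 7 = 28 days (Cycles 1 to 6) or 6 × 7 = 42 days (Cycle 7 on). This limit appears twice, and one of the two statements allows continuation after consulting the sponsor.
- Permanent stop for a Grade 4 infusion reaction or a third Grade 3 one.
- Permanent stop of all study treatment if related events delay every study drug for 8 weeks or more.

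None of these names the listed skin events as a reason to stop. By contrast, 4.1.5.1 stops nivolumab permanently for Grade 4 drug-related events, with exceptions that include no skin event. Daratumumab has no counterpart.

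**What is left uncovered when daratumumab is suspected.**
1. An event of Grade 3 or above that is not an infusion reaction and recovers to Grade 2 or baseline within the hold limit: restart is allowed.
2. A bullous or exfoliative rash below Grade 3: the item lists these without a grade, but the daratumumab delay criterion for non-hematologic toxicity starts at Grade 3, so even the delay is not triggered.

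**The case against.** The strongest reply is that other rules already protect the subject. Section 3.5 obliges a stop when the investigator judges that continuing is not in the subject's interest, and a permissive sentence in 3.5.1 does not override it. Section 4.1.5.2 adds the delay and the hold limits. In the ND arm, continuing daratumumab after nivolumab is stopped needs agreement of the investigator and the medical monitor, plus clinical benefit. Infusion reactions have graded rules in 3.4.1.4. The documents stress infusion reactions as the daratumumab risk and do not say that it causes the listed skin events. Appendix 5 and the daratumumab prescribing information were not available and may add guidance.

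Most of this stands, and it is why the point is minor. It does not close the gap. The protections are discretionary, temporary or confined to infusion reactions. The medical-monitor condition attaches to stopping nivolumab, so it does not reach the D arm. Sections 3.5 and 4.1.5.1 cite Appendix 5 for immune-mediated events, which 3.5 ties to nivolumab.

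One could also read treatment related as meaning related to nivolumab or pomalidomide. The neighbouring items, which do name a drug, argue against that. Even on that reading, 4.1.5.2 would still contain no permanent daratumumab stop for these events.

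A reader might go further and infer that the item acts on the wrong drug throughout Cohort B and costs ND subjects nivolumab without cause. The documents do not support that. In the D arm it acts on no drug at all. Once nivolumab has started, either antibody may be responsible, and stopping nivolumab is a reasonable default. Before it starts, applying a duty to discontinue to a drug not yet given is an inference. Section 4.1.5.1 separately stops nivolumab for Grade 4 drug-related events and for Grade 3 drug-related hypersensitivity, also without naming the causal drug in those criteria, so such a loss could not be put down to this item alone. Starting a checkpoint inhibitor soon after a severe skin reaction is also not clearly safer.

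**Conclusion.** Wrong as written, as a minor safety rule. The 3.5.1 item permits daratumumab without regard to cause, and nothing in 4.1.5.2 imposes a permanent stop for the listed skin events. For about 20 of 60 Cohort B subjects the mandatory half has no content. For about 40 it controls nivolumab but not daratumumab. The practical exposure is confined to the two routes set out above: quick recovery followed by restart, and a listed rash below Grade 3.

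The conclusion rests on the ordinary reading of treatment related as any study treatment, on the planned 2:1 allocation, and on the supplied text alone. No event rate is given, so no probability is stated; few events are assumed. Nothing is claimed about lost nivolumab doses or about efficacy.

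**What to change.** Make two wording changes by protocol amendment.

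1. In 3.5.1, state that daratumumab may continue only if it is not a suspected cause of the event.
2. In the permanent-stop list of 4.1.5.2, add the following when related to daratumumab, for both Cohort B arms: Stevens Johnson syndrome, toxic epidermal necrolysis, Grade 4 rash, and bullous or exfoliative rash.

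Leave angioedema that occurs as a daratumumab infusion reaction to the graded rules in 3.4.1.4 and the laryngeal-edema restart condition in 4.1.5.2. Keep the nivolumab stop as it is, in line with 4.1.5.1.

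No extra subjects or procedures are needed. The downside is that attribution rests on the investigator, so a few subjects may lose daratumumab when it was not the cause. In the D arm that means losing the only study antibody.

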3.6 Post Study Drug Follow-up in Nivolumab/Daratumumab Cohorts (Cohorts A and B)

PFS and OS are efficacy endpoints of the study. Post treatment study follow-up is essential to preserving subject safety and the integrity of the study. Subjects who discontinue study treatment prior to progression must continue to be followed for collection of protocol-defined PFS.

Subjects who discontinue study therapy may also continue to be followed for OS data.

BMS may request that survival data be collected on all treated/randomized subjects outside of the protocol-defined window. At the time of this request, each subject will be contacted to determine their survival status unless the subject has withdrawn consent for all contacts or is lost to follow-up.

3.6.1 Withdrawal of Consent

Subjects who request to discontinue study drug will remain in the study and must continue to be followed for protocol specified follow-up procedures. The only exception to this is when a subject specifically withdraws consent for any further contact with him/her or persons previously authorized by subject to provide this information. Subjects should notify the investigator of the decision to withdraw consent from future follow-up in writing, whenever possible. The withdrawal of consent should be explained in detail in the medical records by the investigator, as to whether the withdrawal is from further treatment with study drug only or also from study procedures and/or post treatment study follow-up, and entered on the appropriate CRF page. In the event that vital status (whether the subject is alive or dead) is being measured, publicly available information should be used to determine vital status only as appropriately directed in accordance with local law.

3.6.2 Lost to Follow-Up

All reasonable efforts must be made to locate subjects to determine and report their ongoing status. This includes follow-up with persons authorized by the subject as noted above. Lost to follow-up is defined by the inability to reach the subject after a minimum of three documented phone calls, faxes, or emails as well as lack of response by subject to one registered mail letter. All attempts should be documented in the subject's medical records. If it is determined that the subject has died, the site will use permissible local methods to obtain the date and cause of death.

If investigator's use of third-party representative to assist in the follow-up portion of the study has been included in the subject's informed consent, then the investigator may use a Sponsor-retained third-party representative to assist site staff with obtaining subject's contact

information or other public vital status data necessary to complete the follow-up portion of the study. The site staff and representative will consult publicly available sources, such as public health registries and databases, in order to obtain updated contact information. If after all attempts, the subject remains lost to follow-up, then the last known alive date as determined by the investigator should be reported and documented in the subject's medical records.

4 TREATMENTS

Study drugs include both Noninvestigational (NIMP) and Investigational Medicinal Products (IMP) and can consist of the following:

- All products, active or placebo, being tested or used as a comparator in a clinical trial
- Study required premedication, and
- Other drugs administered as part of the study that are critical to claims of efficacy (eg, backbone therapy, rescue medications)

Investigational Product

An investigational product, also known as investigational medicinal product in some regions, is defined as a pharmaceutical form of an active substance or placebo being tested or used as a reference in a clinical study, including products already with a marketing authorization but used or assembled (formulated or packaged) differently than the authorized form, or used for an unauthorized indication, or when used to gain further information about the authorized form.

The investigational product should be stored in a secure area according to local regulations. It is the responsibility of the investigator to ensure that investigational product is only dispensed to study subjects. The investigational product must be dispensed only from official study sites by authorized personnel according to local regulations.

In this protocol, investigational product(s) is/are: nivolumab and daratumumab.

Noninvestigational Product

Other medications used as support or escape medication for preventative, diagnostic, or therapeutic reasons, as components of the standard of care for a given diagnosis, may be considered as noninvestigational products.

Handling and Dispensing

The product storage manager should ensure that the study drug is stored in accordance with the environmental conditions (temperature, light, and humidity) as determined by the sponsor. If concerns regarding the quality or appearance of the study drug arise, do not dispense the study drug and contact the sponsor immediately.

Investigational product documentation must be maintained that includes all processes required to ensure drug is accurately administered. This includes documentation of drug storage, administration and, as applicable, storage temperatures, reconstitution, and use of required processes (eg, required diluents, administration sets).

For nivolumab and daratumumab, please refer to the current IB/pharmacy reference sheets for storage, handling and preparation instructions.

